Study objectives	
Primary Objective
 
Absolute pain score 24h after surgery, assessed by 100mm visual analogue score (VAS).
 
Secondary Objectives
 
Minimal Clinically Important Difference [MCID] in visual analogue score; VAS adjusted for pain severity; postoperative morbidity; opioid use; heart rate variability [explanatory variable].

Study design	Phase II, single-centre, two-arm, parallel group randomised controlled trial
Setting	Surgical services of hospitals undertaking major trauma orthopaedic surgery.
Participants	
Inclusion criteria
 
 • Scheduled to undergo major elective or urgent (not requiring intervention in <24h) noncardiac (orthopaedic) surgery under general and/or spinal anaesthesia, expected to take >120 minutes from the induction of anaesthesia. • American society of Anaesthesiologists (ASA) grade I–III. • Aged 18 years and over. 
Exclusion criteria
 
 • Requiring invasive mechanical ventilation and/or new renal replacement therapy during hospitalization. • Cardiac arrhythmia requiring therapy prior to/during hospitalization. • Dementia. • Cancer requiring active/ongoing therapy. • Postural orthostatic tachycardia syndrome. • Lower limb neuromuscular disorders. • Auricular dermatitis. • Day-case surgery, not requiring overnight hospital admission.
Interventions	
Sham Group: Patients randomised to receive sham treatment will receive no current via the bilateral auricular leads for 50 minutes.
 
Stimulation Group: Patients randomised to receive stimulation will receive a sub-threshold current via the bilateral auricular leads for 50 minutes.

Primary outcome measure	The primary outcome is absolute pain score 24h after surgery, assessed using the 100mm visual analogue score.

Outcome measures

Primary outcome measure

The primary outcome will be the absolute VAS pain score 24h after surgery.

Secondary outcome measures

Minimally Clinical Important Difference: The proportion of participants who achieve a minimally clinical relevant reduction >10mm using the 100 mm pain Visual Analogue Score will be compared before and after the period of stimulation in each group, before and after surgery.[1]

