VAS stratified by pain intensity: Absolute changes in pain score before and after sham/stimulation will be compared before and after the period of stimulation in each group before and after surgery, stratifying for mild, moderate, and severe pain intensity before the intervention. A pain VAS score of 30, 70, and 100 indicates the upper boundaries of mild, moderate, and severe pain intensity.[1]

Postoperative morbidity: Defined by the Post Operative Morbidity Survey (POMS) before (preoperative) and after (postoperative days 3 and 7) surgery. The POMS is an 18-item survey which examines nine domains (pulmonary, infection, renal, gastrointestinal, cardiovascular, neurological, haematological, wound, pain) of postoperative morbidity.[2] The POMS is a reliable and valid measure of short-term postoperative morbidity following major surgery.²⁰ The hospital electronic patient management system will be used to prospectively record POMS on postoperative days 0 (preoperative), 3 and 7. Clavien-Dindo grades for complications during hospital stay will also be reported.

Opiate use: Opiate consumption [expressed as morphine equivalents] before and for three days after surgery.

Explanatory measures

Autonomic function, as assessed by time and frequency domain measures of heart rate variability 10 minutes before and 10 minutes after each stimulation session, before and after surgery.[3]

Sample size and randomisation

Sample size calculation

Consensus perioperative guidelines recommend that the Visual Analogue Score should be used to assess pain intensity.[4] 72 patients are required to have a 90% chance of detecting, significant at the 1% level, a decrease in mean VAS (the primary outcome measure) from 34mm in the control group to 23mm in the experimental group after surgery (standard deviation of outcome 12mm). Allowing for 10% dropout per group, a final sample size of 86 participants is required, analysed by intention to treat.

Randomisation procedure

Randomisation will occur after the participant has provided informed consent before the surgical procedure is due to start. Participants are randomly assigned (1:1) by block randomisation to receive stimulation or sham stimulation to ensure a balance in sample size across groups over time (Power

Analysis & Sample Size (PASS) 2021, Utah, USA). Investigators will log on to a secure web-based randomisation file to obtain a unique patient identification number and allocation to a treatment group.

Analysis methods

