General analysis principles

Analyses will follow the intention-to-treat principle: all randomised patients with a recorded outcome will be included in the analysis and analysed according to the treatment to which they were randomised [5, 6]. Patients will be included in the analysis, regardless of whether the treatment they received was compliant with the protocol. Definitions of what constitutes a recorded outcome for each outcome can be found in Appendix 1. Patients with missing outcome data will be excluded from the analysis. Missing data for baseline covariates to be included in the analysis model will be accounted for using mean imputation for continuous variables and the missing indicator approach will be used for missing data for categorical variables [7, 8].

For the analysis of the primary outcome, each secondary outcome, and all process measures, we will present the following information:

The number of patients included in each analysis, by treatment group

A summary statistic of the outcome (e.g. mean (SD), number (%)), by treatment group

The estimated treatment effect

A 95% confidence interval for the estimated treatment effect

A two-sided p-value

For all analyses, a significance level of 5% will be used.

Representativeness of patients

A log of eligible patients not recruited to the trial will be kept. Reasons for non-participation will be categorised and summarised. Participation in the trial, treatment allocation and completeness of follow-up will be illustrated by a CONSORT flow diagram [9].

Baseline characteristics

Baseline characteristics will be summarised for each treatment group by the mean and standard deviation or median and interquartile range for continuous variables, and the number and percent for categorical variables. The following baseline characteristics will be summarised by treatment group:

- Demographic: age (years), gender (male/female)
- Co-morbid disease: Hypertension; Ischaemic heart disease; Cardiac failure; Cardiac valvular disease
- Stroke/TIA; Peripheral vascular disease; Diabetes mellitus, type I; Diabetes mellitus, type II ; COPD; Asthma
Smoker; Interstitial or other respiratory disease; Liver cirrhosis; GI pathology-other; Osteoarthritis;
Rheumatoid arthritis; Inflammatory disease; Active cancer; Previous cancer
- ASA grade

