- Medications: Statin; Anticoagulant; Antiplatelet; Beta-blocker; Calcium channel antagonist; Heart rate limiting calcium channel antagonist; Doxazosin; Diuretic; Nitrate; Angiotensin converting enzyme inhibitors; Angiotensin II Receptor Blockers; Other hypertensives; Other heart failure Rx; Digoxin/anti-arrhythmic; Other Rx Asthma Rx; Opioids-oral; Opioids- parental; NSAIDs; Paracetamol' Steroids; Metformin; Insulin; Any other diabetic medication
- Pre-operative blood test results (within 1 week before surgery or most recent): Haemoglobin; Serum Albumin; Creatinine; white cell count; Neutrophil count; Lymphocyte count; CRP
- Anxiety: GAD-7 and Amsterdam preoperative anxiety score.

Analysis software

All analyses will be conducted in NCSS 2021 (NCSS 2021 Statistical Software (2021). NCSS, LLC. Kaysville, Utah, USA, ncss.com/software/ncss).

Analysis of primary outcome

Primary analysis

Difference in absolute pain score 24h after surgery, assessed by 100mm visual analogue score (VAS), under the ITT principle [10]. Repeat-measures ANOVA will be used to compare VAS before versus after stimulation/sham, with post hoc Tukey-Kramer testing.

Analysis of secondary outcomes

Minimally clinical relevant reduction before and 24h after surgery: The proportion of participants who achieve a minimally clinical relevant reduction >10mm using the 100 mm pain Visual Analogue Score will be compared before and after the period of stimulation in each group, before and after surgery.[1] Paired t-test will compare between sham and stimulation groups.

VAS stratified by pain intensity: Absolute changes in pain score before and after sham/stimulation will be compared before and after the period of stimulation in each group before and after surgery, stratifying for mild, moderate, and severe pain intensity before the intervention. Repeat-measures ANOVA will be used to compare VAS before versus after stimulation/sham, with post hoc Tukey-Kramer testing.

Postoperative morbidity: Absence of POMS will be compared between groups serially [time to become free of morbidity after surgery]. Individual POMS will be reported in a separate table but not tested formally.

Opiate use: Opiate consumption [expressed as morphine equivalents] will be presented before and for three days after surgery, between stimulation/sham, but not tested formally.

Explanatory measures

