Appendix 1: Derived outcomes and variables

Variables

Primary outcome

VAS 24h after surgery: Expressed as 0-100mm.

Secondary outcomes

Minimally Clinical Important Difference: Expressed as 0-100mm.

[figure not shown]
VAS stratified by pain intensity: Expressed as 0-100mm.

Postoperative morbidity: 18-item survey reporting nine domains (pulmonary, infection, renal, gastrointestinal, cardiovascular, neurological, haematological, wound, pain) of postoperative morbidity.[2]

Opiate use: Opiate consumption – morphine equivalents [mean SD]

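### The responder outcome (VAS fall above 10 mm) is a proportion in two unmatched arms, but the SAP compares the arms with a paired t-test

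*SAP*

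**What the plan says.** The SAP's summary table describes a "Phase II, single-centre, two-arm, parallel group randomised controlled trial". Under Randomisation procedure, "Participants are randomly assigned (1:1) by block randomisation to receive stimulation or sham stimulation". No matching or crossover is described.

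The first-listed secondary outcome is "The proportion of participants who achieve a minimally clinical relevant reduction >10mm using the 100 mm pain Visual Analogue Score". It appears in those terms under both Secondary outcome measures and Analysis of secondary outcomes, and is assessed around the stimulation period before and after surgery. The analysis section then names one test: "Paired t-test will compare between sham and stimulation groups". No other test is given for this outcome.

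Appendix 1 describes the variable differently: "Minimally Clinical Important Difference: Expressed as 0-100mm".

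General analysis principles promises, for every secondary outcome, an estimated effect, "A 95% confidence interval for the estimated treatment effect" and "A two-sided p-value", judged at 5%. Dummy Table 4 in Appendix 3 has an MCID row with columns for the effect, its interval and the p-value, so a formal between-arm result is planned.

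**The concern.** A paired t-test analyses within-pair differences and needs a real link between the two members of each pair. Here the two values would come from two unrelated patients, one per arm, so the only available link is the order of rows in the data file. Re-sorting the file leaves the responder counts and the risk difference unchanged but alters the standard error, and with it the p-value and confidence interval.

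The test also needs equal numbers in the two arms. General analysis principles drops patients with missing outcomes, and the sample size section allows for 10% dropout per group, so unequal arms are likely. A paired test would then have to discard patients who have a recorded outcome, against the SAP's own rule that all of them are included.

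At stake is the between-arm result for a formally reported secondary outcome. It would either depend on file order or come from a replacement test chosen after the data are seen. The same responder status feeds the planned exploratory analysis of autonomic parameters and MCID achievement, which needs an unambiguous yes/no definition.

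**Working it through.** **Inputs from the SAP.** Two independent arms, 1:1; 72 evaluable patients, so 72/2 = 36 per arm; two-sided tests at 5%. The SAP gives no responder rate or power for this outcome, so the counts below are assumptions, shown over a range.

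**The plan's own figure.** For the primary outcome (34 vs 23 mm, SD 12, two-sided 1%, 90% power), n per arm = 2 × (2.576 + 1.282)² × 12² / 11² = 35.4, rounded up to 36, total 72. This reproduces and confirms that the trial was sized for two independent groups.

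**How the paired test depends on row order.** Score each patient 1 (fall above 10 mm) or 0. Let there be *a* sham and *b* stimulation responders, *n* = 36 rows, and *k* rows in which both patients happen to be responders. Then:

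- mean difference = (*b* − *a*)/*n*, which does not involve *k*
- variance of the differences = [*a* + *b* − 2*k* − (*b* − *a*)²/*n*] / (*n* − 1), which does
- *t* = mean difference / √(variance/*n*), on 35 degrees of freedom

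Row order fixes *k* and nothing else. With random ordering *k* is hypergeometric, so the full range of p and the share of orders below 0.05 can be computed exactly.

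**Worked case, 11 vs 19.** Mean difference = 8/36 = 0.222.

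- *k* = 0: variance = (30 − 64/36)/35 = 0.806; *t* = 1.485; p = 0.147
- *k* = 6: variance = (18 − 64/36)/35 = 0.463; *t* = 1.958; p = 0.058
- *k* = 7: variance = (16 − 64/36)/35 = 0.406; *t* = 2.092; p = 0.044
- *k* = 11: variance = (8 − 64/36)/35 = 0.178; *t* = 3.162; p = 0.003

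Moving from *k* = 6 to *k* = 7, which swapping two rows within one arm can do, crosses 0.05. The probability that *k* ≥ 7 is 0.31.

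**Independent-groups analysis of the same data.** Pooled proportion 30/72 = 0.417; z² = 0.222² / (0.417 × 0.583 × 2/36) = 3.66; chi-square p = 0.056. Fisher's exact p = 0.094. Risk difference 22.2 points, standard error √(0.306 × 0.694/36 + 0.528 × 0.472/36) = 0.113, Wald 95% interval 0.03 to 44.4 points. None of these depends on row order.

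**Range over assumed counts, 36 per arm.**

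| Sham vs stimulation responders | Paired p, lowest to highest | Random orders with p < 0.05 | Chi-square p | Fisher p |
|---|---|---|---|---|
| 13 vs 20 | 0.006 to 0.228 | 1% | 0.098 | 0.155 |
| 11 vs 18 | 0.006 to 0.198 | 1.4% | 0.093 | 0.149 |
| 11 vs 19 | 0.003 to 0.147 | 31% | 0.056 | 0.094 |
| 11 vs 20 | 0.002 to 0.107 | 88% | 0.032 | 0.056 |
| 9 vs 18 | 0.002 to 0.083 | 94% | 0.028 | 0.051 |

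For 13 vs 20, 5,000 random orders gave p from 0.017 to 0.198 with median 0.109; the table shows the full attainable range.

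**Unequal arms.** With 36 and 35 patients the paired test returns an error.

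**Type I error under random pairing.** In 40,000 simulated trials per setting with equal true rates in both arms, the paired test rejected at 5% in 4.4%, 4.7% and 5.1% of trials for response rates of 20%, 30% and 50%.

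**The case against.** The strongest reply concerns consequence. This is one of several secondary outcomes in a Phase II trial, with no stated hierarchy, and the primary analysis is untouched. If row order is truly random, the test keeps roughly its nominal size and the risk difference itself does not move. How often significance flips depends heavily on the assumed counts: at 13 vs 20 only about 1% of orders fall below 0.05 and the median p of 0.109 is close to the chi-square value. If the arms end up unequal, software will refuse the test and the error will be noticed. All of this stands, and it limits the size of the harm. It does not make the test right: file order need not be random, and an error noticed at analysis leads to an unplanned choice of test.

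The second reply is that the preceding sentence speaks of comparisons before and after stimulation within each group, where pairing on the VAS in mm would be natural, so two comparisons may have been run together. That is a plausible origin, but the sentence naming the test says that it compares the two groups. If a within-arm test was meant, the outcome has no between-arm test at all, although Table 4 calls for one. A responder proportion also has no before and after value, because the fall in VAS is already the change.

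Third, the Appendix 1 entry may only describe the scale of the underlying VAS. That is a fair reading, and the entry is more an imprecision than a rival definition. Analysing the outcome in mm would not help, since pairing independent arms is wrong for a continuous score too.

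**Conclusion.** The point holds. The SAP prescribes a paired test for two unmatched arms, and nothing elsewhere in it corrects this. At 36 per arm and equal numbers, the p-value is set partly by row order: across the assumed counts the attainable range spans 0.05 every time, and the share of orders below 0.05 runs from about 1% to 94%. With unequal arms the test cannot be run on all patients with a recorded outcome.

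The responder counts are assumptions. The conclusion that the test is wrong does not rest on them; only the size of the illustration does. The damage is confined to a secondary outcome and is one of arbitrariness and reproducibility, not of inflated false positives under random pairing. It should be corrected before the data are analysed, because the purpose of the SAP is to fix this choice in advance.

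**What to change.** - In Appendix 1, define the outcome as binary: VAS before the session minus VAS after it above 10 mm, yes or no, separately for the preoperative and the postoperative session.
- Delete the paired t-test. For each session, compare arms by the risk difference with a 95% confidence interval (for example Newcombe) and Fisher's exact test, or by logistic regression on arm adjusted for pre-session VAS. Any standard independent-groups method for proportions would do, but the test and the interval should be named together: in the 11 vs 19 example the Wald interval just excludes zero while chi-square gives 0.056.
- If a within-arm before-after description of VAS in mm is also wanted, state it separately and say that it is not the comparison of stimulation with sham.
- Give the MCID row of Table 4 one line per session.

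The cost is SAP wording only; no new data are needed and the sample size does not change.

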≥1 treatment deviation		
Current before		
Current after		
Other deviation		

Table 4: Primary and secondary outcomes.

Outcomes	Number of patients with available data and included in analysis - no. (%)		Summary measure		Treatment effect (95% CI)	P-value
	Sham (n=XX)	Stimulation (n=XX)	Sham	Stimulation		
Primary outcome						
VAS 24h after surgery						
Secondary outcomes						
MCID						
VAS before surgery						
VAS [pain intensity]						
Opiate use						

Table 5: PostOperative Morbidity survey: reported before surgery, 3 and 7 days after surgery.

Complication	Number of patients with available data - no. (%)		Summary measure	
	Sham (n=XX)	Stimulation (n=XX)	Sham	Stimulation
De novo requirement for supplemental oxygen.				
Respiratory support.				
Currently on antibiotics.				
Temperature >38°C/ blood cultures in last 24h.				
Oliguria (< 500 mL/day),				
Serum creatinine (>30% from baseline value)				
Unable to tolerate normal enteral diet				
Nausea/vomiting.				
Myocardial infarction or ischemia				
Hypotension (drug therapy/fluid >200 mL/h)				
Atrial or ventricular arrhythmia				
Pulmonary edema				

De novo focal neurological deficit				
Coma.				
Confusion/delirium.				
Wound dehiscence requiring surgical exploration				
Wound drainage/pus.				
Blood, platelets, fresh frozen plasma or cryoprecipitate.				
Surgical wound pain-parenteral opiates				
Regional anesthesia.				
Not mobilising alone				
None				

Table 6: Process measures

Process measures	Number of patients with available data - no. (%)		Summary measure	
	Sham (n=XX)	Stimulation (n=XX)	Sham	Stimulation
Re-admission to hospital within 30 days of surgery – no. (%)				
Duration of hospital stay after surgery (days) - Median (IQR)				
Number of patients admitted to a critical care unit - no. (%)				

Table 7: Adverse events

Adverse Events - no. (%)	Sham (n=XX)	Stimulaton (n=XX)
Patients with ≥ 1 adverse event		
Total number of adverse events		
Type of adverse events		
Arrhythmia ^a		
Headache		
Pain ^b		
Skin irritation at the stimulation site		
Dizziness		
Other		
None		

^a Defined as clinically detected arrhythmia during or after day of intervention.

^b Defined as localised pain to auricular region

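### Freedom from POMS morbidity is described as a time but is seen at only two postoperative assessments, and the SAP does not say how patients discharged before an assessment are scored

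*SAP*

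**What the plan says.** **Analysis of secondary outcomes, Postoperative morbidity:** "Absence of POMS will be compared between groups serially [time to become free of morbidity after surgery". Individual POMS items are tabulated and not tested. No test, model, censoring rule, or rule for death or relapse is given.

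**Secondary outcome measures, Postoperative morbidity:** the hospital's electronic system "will be used to prospectively record POMS on postoperative days 0 (preoperative), 3 and 7". That makes one preoperative and two postoperative assessments. No source of POMS data after discharge is named.

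**General analysis principles:** "Patients with missing outcome data will be excluded from the analysis". The same section asks for an effect estimate, a 95% confidence interval and a p-value for each secondary outcome, and states: "Definitions of what constitutes a recorded outcome for each outcome can be found in Appendix 1".

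**Appendix 1:** the entry is "Postoperative morbidity: 18-item survey reporting nine domains", followed by the list of domains. It describes the instrument and does not say what counts as a recorded POMS.

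**Sensitivity analysis:** missing data are addressed for the primary outcome only, if more than 5% is missing.

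**Appendix 3:** Table 5 sets out the POMS rows, including "Not mobilising alone", and closes with a row for none. Table 4, which holds treatment effects and p-values, has no POMS row. It does have one for opiate use, which the SAP says is not formally tested.

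**The concern.** There are three linked problems.

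1. **The quantity does not match the data.** A time to freedom from morbidity cannot be observed at two snapshots. If an analyst took the bracketed phrase at face value and used an ordinary time-to-event method, the apparent timing would come from the assessment schedule.

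2. **Early discharge has no rule.** Eligibility requires only an overnight stay, so patients may leave before day 3, and more may leave before day 7. If they have no POMS record and missing outcomes are excluded, each comparison is made among patients still in hospital. Staying in hospital happens after randomisation and may depend on recovery, and so on treatment. The randomised comparison is lost and the denominator shrinks with time.

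3. **Free is not defined in one way.** The text and Appendix 1 describe 18 items in nine domains, and Table 5 does not match that.

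At stake is the estimate, and possibly the direction, of a named secondary outcome, with the choice left to the analyst after the data are seen.

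**Working it through.** **What the SAP supplies.** It gives no POMS rate, discharge share or expected length of stay, so there is no plan figure to reproduce. The only number used from it is the sample size: 86 randomised 1:1, so 86 / 2 = 43 per arm. All other inputs below are assumptions.

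**Step 1: what two assessments can show.**

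| Day 3 | Day 7 | Time to freedom |
|---|---|---|
| free | free | by day 3 |
| morbid | free | between day 3 and day 7 |
| morbid | morbid | after day 7 |
| free | morbid | undefined without a relapse rule |

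The time is interval-censored, with two possible event times, and one of the four patterns has no place in it.

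**Step 2: the effect of dropping discharged patients.** Let d be the share of an arm discharged before the assessment and f the share free among those still in hospital. If discharged patients are taken as free:

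- all randomised: P(free) = d + (1 − d) × f
- excluding the discharged: P(free) = f

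*Day 7, assumed counts, 43 per arm.* Stimulation: 30 discharged, 13 in hospital, 8 of them morbid. Sham: 20 discharged, 23 in hospital, 12 of them morbid.

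- all randomised, morbid: 8/43 = 18.6% v 12/43 = 27.9%, which favours stimulation
- inpatients only, morbid: 8/13 = 61.5% v 12/23 = 52.2%, which favours sham

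*Day 3, assumed counts, 43 per arm.* Stimulation: 17 discharged, 7 of 26 inpatients free. Sham: 9 discharged, 12 of 34 inpatients free.

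- all randomised, free: (17 + 7)/43 = 55.8% v (9 + 12)/43 = 48.8%, difference +7.0 points
- inpatients only, free: 7/26 = 26.9% v 12/34 = 35.3%, difference −8.4 points

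**Step 3: when the direction changes and when it does not** (stimulation v sham, share free).

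- d = 40% v 20%, f = 30% v 35%. All randomised: 0.40 + 0.60 × 0.30 = 58% v 0.20 + 0.80 × 0.35 = 48%, +10 points. Inpatients only: −5 points.
- d = 30% in both arms, f = 35% v 25%. All randomised: 0.30 + 0.70 × 0.35 = 54.5% v 0.30 + 0.70 × 0.25 = 47.5%, +7 points. Inpatients only: +10 points. The direction holds.

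A simulation with exponential recovery times (means 3 v 4 days), no relapse, and an exponential lag from recovery to discharge gave:

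| Mean lag (stimulation, sham) | Day | Free, all randomised | Free, inpatients only |
|---|---|---|---|
| 1 day, 1 day | 3 | 63.1% v 52.9% | 30.0% v 23.0% |
| 1 day, 1 day | 7 | 90.3% v 82.7% | 33.1% v 25.1% |
| 0.5 day, 1 day | 3 | 63.2% v 52.8% | 16.6% v 22.9% |
| 0.5 day, 1 day | 7 | 90.3% v 82.6% | 16.5% v 24.8% |

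In these runs faster recovery alone did not turn the result round. A difference between arms in the lag from recovery to discharge did. In the last row 88.4% and 76.9% have left by day 7, so the inpatient comparison would rest on about 43 × 0.116 = 5 and 43 × 0.231 = 10 patients.

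**Step 4: the Table 5 rows.** There are 21 rows above the none row, against 18 stated items. The mobility row matches none of the nine domain names. Without it 21 − 1 = 20 rows remain, so removing it does not by itself reconcile the counts.

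**The case against.** The strongest reply is that the SAP does not do what it might be accused of. Five points deserve weight.

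- **Exclusion of discharged patients is not written.** A reader might infer that the SAP orders it. It excludes patients with missing outcomes and never says that discharge makes POMS missing. The protocol may settle the scoring. This stands, and the defect is therefore an absent rule. It still matters, because the SAP sends the reader to Appendix 1 for the definition and Appendix 1 does not give it.
- **Discharged patients need not have recovered.** No discharge criteria are stated, and Table 6 plans to report readmission within 30 days. This stands.
- **Reversal is not inevitable.** It needs discharge relative to recovery to differ by arm. In the day 7 illustration only the point estimates change sides. The Wald 95% intervals for the difference in morbidity are about −27 to +8 points for all randomised patients and −24 to +43 points for inpatients. This stands, though loss of the randomised comparison does not depend on reversal.
- **No survival method is named.** Serial comparison at days 3 and 7 is close to what is recommended here, and the timing phrase is a bracketed gloss. A charge of false precision is therefore conditional on how the gloss is read. The fair complaint is that the method is unnamed and the gloss ambiguous.
- **Nothing says that the mobility row enters the tested outcome.** Table 5 is an item-level table that is not tested, and table rows need not equal survey items. To infer that lower-limb patients would be kept from ever counting as free goes beyond the document. What remains is an inconsistency in the definition.

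**Conclusion.** The point holds as a gap in specification. Two postoperative assessments support proportions free at each, or an interval-censored analysis, and not an observed time to freedom. The SAP fixes no rule for patients who leave hospital before an assessment. Its general rule, read literally with a hospital data source, would limit the comparison to inpatients.

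The resulting bias cannot be sized from the SAP. The illustrations show that it can be large enough to turn 19% v 28% morbid into 62% v 52%. They rest on assumed counts, on discharged patients being free of morbidity, and on discharge relative to recovery differing between arms. Where discharge shares, or the lag from recovery to discharge, were equal in the scenarios tried, the direction held. The documents do not support the stronger conclusion that the planned analysis will show harm where there is benefit.

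This concerns a secondary outcome and leaves the primary analysis untouched. It is a cheap improvement, best made before the data are seen.

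**What to change.** Replace the sentence on absence of POMS in Analysis of secondary outcomes with:

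> The proportion free of POMS morbidity will be compared between arms at day 3 and at day 7 (risk difference, 95% CI) in all randomised patients. Discharged alive before the assessment counts as free, and death counts as not free. A patient readmitted and in hospital at the assessment is scored on the inpatient record. Inpatients with no POMS recorded are treated as missing and their number is reported by arm.

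Then:

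- add two sensitivity analyses, one among inpatients only and one with readmitted patients counted as not free;
- define free by the nine domains in Secondary outcome measures, repeat this in Appendix 1, reconcile the Table 5 rows with it, and report mobility separately;
- add POMS at day 3 and day 7 to Table 4, with the p-value that General analysis principles requires and the test named.

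**Cost.** The change is SAP wording and table shells. Length of stay and 30-day readmission are already planned in Table 6. The dates of readmission and of any death must be available to apply the rules. The main downside is that morbidity after discharge is assumed absent; the two sensitivity analyses show how far the result depends on how discharged and readmitted patients are scored.
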